10.16.2 Maximum Reduction

For NPRS scores, maximum reduction from baseline (that is, maximum negative change from baseline) for a subject within each study period will be flagged. Time to maximum change in days and week at which maximum reduction was attained will be included.

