11.6.1.2 Mixed Effect Regression Model

A mixed effects regression model using a covariance pattern will be fitted to the absolute change from baseline mean NPRS scores at weeks 1, 2, 3 and 4 within each treatment period for the PP population. This analysis will provide the results for the primary efficacy endpoint (change from baseline to week 4) and for the secondary endpoint (change from baseline to weeks 1, 2 and 3).

The model will have fixed effects for period, week, treatment and the interaction between week and treatment. Baseline mean pain score within each period by treatment combination will be included as a covariate. A random effect for subject will be included to capture the repeated measures nature of the design.

Least squares means and corresponding 95% confidence intervals (CI) will be presented for the mean change from baseline for LAT8881, Placebo and difference between LAT8881 vs. placebo at each visit.

P-values for testing the null hypothesis that the difference in least squares means between LAT8881 and placebo at each visit is 0 will be declared statistically significant if the p-value < 0.05.

The covariance pattern will take into account the covariance between observations in different treatment periods and the covariance between observations within the same period (i.e between weeks).

```
proc mixed data=;  
class <subject> <study period> <treatment> <week>; model  
<change> = <baseline> <study period> <week> <treatment>;  
random <subject> <subject>*<period>; lsmeans <treatment>  
<week> / pdiff;  
run;
```

The model will also be fitted to the absolute change from baseline in mean NPRS ratings for the FAS population. Extent of sensitivity analyses of missing data patterns to be undertaken will be decided during the blinded review meeting. In DDP: Tables 14.2.2.1 to 14.2.2.2

11.6.1.2.1 *NPRS at timepoints*

A mixed effects regression model using a covariance pattern will be fitted to the absolute change from pre-dose NPRS scores at timepoints 0.5, 1, 2, 4 and 6 hours post-dose at baseline and week 4 visits within each study period for the per-protocol subjects with NPRS collected at timepoints in baseline and week 4 visits.

The model will have fixed effects for period, week, timepoint and the interaction between week and timepoint. Pre-dose pain score within each week will be included as a covariate. A random effect for subject will be included to capture the repeated measures nature of the design.

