11.6.2.3 Maximum change from baseline

Maximum reduction from baseline in NPRS mean scores will be summarized. Number and percentage of subjects will be summarized for the week at which maximum reduction from baseline in NPRS mean scores was reached by treatment overall and within each study period. This will be repeated for Per Protocol and FAS populations.

In DDP: Table 14.2.4.1 to 14.2.4.2

11.6.2.3.1 *Mixed Effects Regression Model*

Mixed effects regression models will be used to compare the maximum reduction from baseline in NPRS mean scores. The model will have fixed effects for period and treatment. Baseline score within each period by treatment combination and time taken to reach maximum reduction will be included as covariates. A random effect for subject will be included to capture the repeated measures nature of the design. Least squares mean changes from baseline and corresponding 95% CI will be presented for LAT8881, Placebo and the difference between LAT8881 vs. placebo overall. The null hypothesis that the difference in least square mean changes from baseline between LAT8881 and placebo across study periods is 0 will be tested. Statistical significance will be declared if the p-value for the difference between treatments < 0.05. In DDP: Table 14.2.4.3, 14.2.4.4

```
proc mixed data=;  
  class <subject> <study period> <treatment>;  
  model <maximum reduction> = <baseline> <study period> <treatment> <time  
  to maximum reduction>;  
  random <subject> <subject>*<period>;  
  lsmeans <treatment>/ pdiff;  
run;
```

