11.6.2.4 Patient reported outcomes

Patient Reported outcomes: BPI, SF-MPQ-2, NPSI, BDI-II, PGIC will be considered for secondary efficacy analyses. All analyses will be repeated for Per-protocol and FAS populations.

11.6.2.4.1 *Descriptive Summaries*

Descriptive summaries of patient reported outcomes (BPI, SF-MPQ-2, NPSI, BDI-II) and absolute change from baseline results will be presented by treatment overall and within each study period. Visits to be included in this table are: Baseline, Week 4.

Descriptive summaries as well as number and percentage of subjects reporting each of the categories in PGIC scale (1 - Substantially worse, 2 - Moderately worse, 3 - Slightly worse, 4 - No change, 5 - Slightly improved, 6 - Moderately improved, 7 - Substantially improved) will be summarized by treatment overall and within each study treatment period.

The summaries will be repeated for Per-Protocol and FAS populations.

In DDP: Tables 14.2.5.1, 14.2.5.2, 14.2.6.1, 14.2.6.2, 14.2.7.1, 14.2.7.2, 14.2.8.1, 14.2.8.2, 14.2.9.1, 14.2.9.2

All patient reported outcomes will be listed.

In DDP: Listing 16.2.6.2 to 16.2.6.6

11.6.2.4.2 *Mixed Effects Regression Model*

Mixed effects regression models will be used to compare the absolute change from baseline to week 4 for the patient reported outcomes (BPI, SF-MPQ-2, NPSI, BDI-II, PGIC). The models will have fixed effects for period and treatment. Baseline score within each period by treatment combination will be included as a covariate for all endpoints except PGIC. A random effect for subject will be included to capture the repeated measures nature of the design. Least squares mean changes from baseline and corresponding 95% CI will be presented for LAT8881, Placebo and the difference between LAT8881 vs. placebo overall. The null hypothesis that the difference in least square mean changes from baseline between LAT8881 and placebo across study periods is 0 will be tested. Statistical significance will be declared if the p-value for the difference between treatments < 0.05.

In DDP: Tables 14.2.5.3, 14.2.5.4, 14.2.6.3, 14.2.6.4, 14.2.7.3, 14.2.7.4, 14.2.8.3, 14.2.8.4, 14.2.9.3, 14.2.9.4

```
proc mixed data=;  
  class <subject> <study period> <treatment>; model  
  <change> = <baseline> <study period> <treatment>;  
  random <subject> <subject>*<period>; lsmeans  
  <treatment>/ pdiff;  
run;  
Note that, PGIC will not have <baseline> in the model statement.
```

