11.6.3 Exploratory Analyses

11.6.3.1

Descriptive summaries of average [REDACTED] will be presented by study period at Baseline and week 4 visits for test and control areas. This summary will be based [REDACTED]

[REDACTED] will be listed by subject.

In DDP: Table 14.2.11.1, Listing 16.2.6.7

11.6.3.1.1 *Mixed Effects Regression Model*

Mixed effects regression models will be used to compare the absolute change from baseline to week

The models will have fixed effects for period and treatment. Baseline score within each period by treatment combination will be included as a covariate. A random effect for subject will be included to capture the repeated measures nature of the design. Least squares mean changes from baseline and corresponding 95% CI will be presented for LAT8881, Placebo and the difference between LAT8881 vs. placebo overall. The null hypothesis that the difference in least square mean changes from baseline between LAT8881 and placebo across study periods is 0 will be tested. Statistical significance will be declared if the p-value for the difference between treatments < 0.05 . See Section 11.6.2.4.2 for SAS program.

In DDP: Table 14.2.11.2

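### SAP 11.6.2.3.1 and 11.6.2.4.2: the code adds a subject-by-period random term that the text does not name; with one record per subject-period it duplicates the residual and leaves zero residual degrees of freedom

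*SAP*

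**What the plan says.** **Text.** SAP 11.6.2.4.2 gives the patient-reported outcome models fixed effects for period and treatment, a baseline covariate (except for PGIC) and a single random effect: "A random effect for subject will be included to capture the repeated measures nature of the design". SAP 11.6.2.3.1 says the same for maximum reduction and adds time to maximum reduction as a covariate.

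**Code.** Under 11.6.2.4.2 the code reads "random <subject> <subject>*<period>; lsmeans", and under 11.6.2.3.1 "random <subject> <subject>*<period>". Neither program states a degrees-of-freedom option. SAP 11.6.3.1.1 (partly redacted) repeats the subject-only text and refers back: "See Section 11.6.2.4.2 for SAS program".

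**Records per subject-period.**
- The patient-reported outcome models "compare the absolute change from baseline to week 4 for the patient reported outcomes", which is one change score per subject and period. PGIC is one rating at the end of each period (SAP 7.2).
- For maximum reduction, SAP 10.16.2 says the value "for a subject within each study period will be flagged", so there is again one per subject and period.
- The weekly NPRS model in SAP 11.6.1.2 uses the same RANDOM statement, but on scores "at weeks 1, 2, 3 and 4 within each treatment period", so it has four records per subject-period.

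**Use.** Both sections promise 95% confidence intervals and declare significance at p < 0.05, in the per-protocol and FAS populations.

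**The concern.** Text and code describe different models, and a programmer cannot follow both. The code version asks for three variances (subject, subject-by-period, residual) from data that can separate only two.

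At stake are six outcomes (five patient-reported outcomes and maximum reduction), each in two populations, so 6 × 2 = 12 fits. Every promised interval and p-value needs a denominator degrees of freedom for the treatment contrast. Treatment is not contained in either listed random term, and no method is stated. A rule that falls back on N minus rank[X Z] would find nothing left. A method that uses the information matrix of the variance parameters would meet a singular matrix. The model would then have to be changed after the output had been seen.

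**Working it through.** **1. Where 44 comes from.** The plan gives no figure for these models, so its 44 evaluable subjects are used. Inputs from Protocol 13.2 and the synopsis: difference 1, SD of change 2, correlation 0.5, two-sided 5%, power 90%, dropout 20%.
- SD of the within-subject difference = √(2 × 2² × (1 − 0.5)) = 2.
- n is 43 by the normal approximation and 44 by the noncentral t (power 0.900 at 44).
- 44 / 0.8 = 55 enrolled.

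Both of the plan's figures reproduce.

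**2. Algebra.** The code implies

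V = σ²_s Z_s Z_s′ + σ²_sp Z_sp Z_sp′ + σ²_e I.

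With one record per subject-period, each row has its own subject-by-period level, so Z_sp Z_sp′ = I and

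V = σ²_s Z_s Z_s′ + (σ²_sp + σ²_e) I.

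Only the sum of the last two variances enters the likelihood. This reads `<period>` in RANDOM and `<study period>` in CLASS as the same factor.

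**3. Residual degrees of freedom, N − rank[X Z], 44 completers, N = 44 × 2 = 88.** The 44 subject columns already span the intercept.

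| Model | Rank, subject only | Residual df | Residual df as coded |
|---|---|---|---|
| PGIC (period, treatment) | 44 + 2 = 46 | 42 | 88 − 88 = 0 |
| BPI, SF-MPQ-2, NPSI, BDI-II (plus baseline) | 44 + 3 = 47 | 41 | 0 |
| Maximum reduction (plus baseline, time to maximum) | 44 + 4 = 48 | 40 | 0 |

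Incomplete data do not help. If 8 subjects lack period 2, N = 80; the baseline-adjusted model has 80 − 47 = 33 with subject only and 80 − 80 = 0 as coded.

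**4. Numerical check.** The documents contain no outcome data, so outcomes were simulated for the baseline-adjusted model with 44 completers. Only the equality across rows carries meaning, not the values. Subject variance was held at 2.

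| Subject-by-period / residual variance | REML log-likelihood | Treatment estimate | SE |
|---|---|---|---|
| 0 / 2 | −103.538035 | −0.825183 | 0.304186 |
| 0.5 / 1.5 | −103.538035 | −0.825183 | 0.304186 |
| 1 / 1 | −103.538035 | −0.825183 | 0.304186 |
| 1.9 / 0.1 | −103.538035 | −0.825183 | 0.304186 |

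The information matrix for the three variances has rank 2 of 3. The likelihood is flat along the split, while the treatment estimate and SE do not move.

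**5. Contrast with the weekly NPRS model.** N = 44 × 2 × 4 = 352. Rank = 88 subject-periods + 3 for week + 3 for week by treatment = 94, so residual df = 258. The information matrix has full rank, 3 of 3, and the term is estimable there.

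**6. SAP 11.6.3.1.1.** If its model has one record per subject-period, step 3 applies with its own N. If two records were stacked (assumed 20 subjects, with area and area-by-treatment terms), N = 80, rank = 40 + 2 = 42, residual df = 38 and the information rank is 3 of 3, so the term would be identified.

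**The case against.** The strongest reply is that the text already gives the right model and the code is only a template. Its placeholders differ between CLASS and RANDOM, and the weekly program omits the week-by-treatment interaction that its own text requires. On that view this is a mismatch between text and code, not a poor choice of analysis. That stands, and it is why the fix is simply to follow the text.

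Zero degrees of freedom would also probably show as a missing or failed test, not as a plausible wrong result. The tests concerned are beyond the primary endpoint, and SAP 8.3 already asks for caution with those. This lowers the severity but does not remove the need to correct the code, because the SAP still commits to intervals and significance statements.

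A reader might infer that the whole model is unidentified, or that the reported treatment effects would depend on starting values. The check does not support this: the subject variance, the sum of the other two variances, the treatment difference and its SE are all determined.

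A reader might also infer that the model in 11.6.3.1.1 is certainly affected. The visible text does not establish that. Its descriptive summaries cover "Baseline and week 4 visits for test and control areas", and the outcome and analysis basis are blacked out. The visible model has no area effect, so one record is plausible, but it remains an assumption.

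**Conclusion.** The point holds, as minor. As printed, the programs in SAP 11.6.2.3.1 and 11.6.2.4.2 contradict their own text and leave 0 residual df, against 40 to 42 with the random subject effect that the text names (44 completers). The consequence is limited to degrees of freedom, a possibly singular fit and reproducibility; the treatment effects are not biased.

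The loss of p-values and intervals is conditional on a df rule that uses residual df, since the SAP names no rule. The conclusion also rests on one record per subject-period, which the SAP text shows for these six outcomes, and on the two period placeholders meaning the same factor. The primary NPRS analysis is not touched.

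**What to change.** - Delete `<subject>*<period>` from the RANDOM statement in SAP 11.6.2.3.1 and 11.6.2.4.2, leaving `random <subject>` as the text says.
- SAP 11.6.3.1.1 inherits the corrected code by its cross-reference. Confirm there that the model has one record per subject-period; if records are stacked by area, give that model its own program.
- Keep the term in the weekly NPRS model (SAP 11.6.1.2).
- Use one name for the period variable in CLASS and RANDOM.
- Optionally, state the degrees-of-freedom method. The deletion alone restores the residual df.

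The cost is one code term in two places, with no change to data, endpoints or sample size. It should be done before database lock.

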11.6.2.5 NPRS and baseline covariates

The mixed effects linear regression model will be repeated for the change from baseline in NPRS scores by including additional covariate: clinical diagnosis (PHN, DPN). Further analyses will be decided and performed in a post-hoc manner post database lock.

In DDP: Table 14.2.10.1

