5.1 Overall study design

This is a randomised, placebo-controlled, double-blind, crossover, multi-site, Phase IIa study to investigate the efficacy and safety of oral LAT8881 in neuropathic pain. The overall study design is shown in Figure 4. Details of the procedures during each phase are described in Section 8.

The pharmacokinetics (PK) of LAT8881 will be investigated on Days 1, 28, 50 and 77 in 15 subjects (PK subjects) at Australian sites. Quantitative sensory testing (QST) will be performed in up to 20 subjects (QST subjects) before the first dose on Days 1 and 50 and after the morning dose on Days 28 and 77. PK subjects will not participate in QST measurements and QST subjects will not participate in PK analyses.

[figure not shown]

Figure 4: Overall study design for LAT-NP-001

Potential subjects will be required to provide written informed consent prior to any study-specific screening procedures being performed. Screening assessments will be performed from Day -28 to Day -1. Subjects deemed likely to be eligible for the trial will be given access to a diary during Screening Stage 1 and training on how to complete it from Days -7 to -1 inclusive (Screening Stage 2, first baseline period). These diary results will be reviewed on Day 1 to confirm that the subject is eligible for the study.

On Day 1, after the first baseline period, eligible subjects will be enrolled and randomised to LAT8881 or placebo. They will receive the investigational medicinal product (IMP) twice daily for four weeks (Days 1 to 28). On the morning of Day 28 they will return to the clinic for their end of first treatment visit and will take an IMP capsule in the morning during their clinic visit. They will take their final IMP dose for this treatment period in the evening.

The first treatment period will be followed by a washout period of two weeks (Days 29 to 42 inclusive) and then a second baseline period of one week (Days 43 to 49 inclusive). Over these days (i.e. Days 29-49 inclusive) subjects will not take any IMP.

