13.8 Analysis of exploratory endpoints

Exploratory analyses will be undertaken to determine the relationship between change in mean NPRS from baseline to the end of four weeks treatment and baseline parameters, such as the clinical diagnosis (PHN or DPN) and baseline QST parameters. The effect of treatment on changes in QST parameters from baseline to the end of four weeks treatment will also be analysed.

The effect of the variability in NPRS scores within the first baseline period on the ability to detect a treatment difference will be examined.

The relationship between plasma LAT8881 and NPRS in PK subjects will also be investigated.

The approaches to these investigative analyses will be detailed in the statistical analysis plan.

14. Study management

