7.5 Exploratory endpoints

1. *Association between change in mean NPRS from baseline to the end of four weeks treatment and selected subject baseline characteristics, including clinical diagnosis and pre-treatment [REDACTED]*
2. *Change from baseline in [REDACTED] [REDACTED] to the end of 4 weeks treatment, in each treatment period*
3. *Correlation between plasma LAT8881 concentration and the change in mean NPRS from baseline to the end of four weeks treatment in PK subjects*
4. *Change in mean NPRS score from baseline to the last week of each treatment period, after omission of subjects with the 25% most variable first baseline NPRS scores*

8 Statistical Methods

Efficacy endpoints will be summarized in a descriptive manner and analyzed using statistical methods described in section 11.7. The level of significance for statistical tests will be 0.05 and all tests will be two-sided. All p-values will be displayed to four decimal places, with p-values less than 0.0001 presented as '<0.0001' and p-values greater than 0.9999 presented as '>0.9999'. All analyses will be done using SAS [REDACTED]

Safety endpoints will be summarised in a descriptive manner.

Continuous data will be reported using the following descriptive statistics:

1. Number of observations (n)

2. Mean and standard deviation (SD)
3. Minimum (min) and maximum (max)
4. Median

Minimum and maximum values will be reported to the precision of the endpoint reported with maximum of three decimal places; the mean will be presented with one decimal place more and the standard deviation two decimal places more than the precision of the endpoint reported. Categorical data will be presented using frequency (n = number of subjects; m = number of events) and percentage (%).

Listings will be provided for all data recorded in eCRF to study subject profiles. All listings will be sorted by treatment sequence, subject ID, study period and date (if applicable). Unscheduled visit data will only be listed and not included in summaries.

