11.7.3.4 Electrocardiogram Assessments

Number and percentage of subjects with overall findings (Normal, Abnormal Not CS and Abnormal CS) will be summarized by treatment overall and within each study period and visit. Percentages will be based on safety population.

In DDP: Table 14.3.6.1

ECG findings will be listed by treatment sequence, subject ID, treatment period and visit.

In DDP: Listing 16.2.9.3

12 Changes to Planned Analyses

- Mixed Effect Regression analyses for change from baseline in NPRS mean scores is combined for weeks 1-4 within the same model, instead of week 4 and weeks 1-3 separately as defined in study protocol.
- McNemar's test is included to compare proportion of subjects achieving $\geq 30\%$ and $\geq 50\%$ reduction in mean NPRS scores across study periods.
- Analysis of covariance is included to see the effect of treatment and placebo in maximum reduction from baseline adjusting for baseline NPRS mean scores and time taken to reach maximum reduction.
- Mixed Effect Regression analyses for change from baseline in NPRS mean scores including clinical diagnosis (PHN, DPN) and baseline [REDACTED] as additional covariates is

considered as secondary analyses instead of exploratory analyses since subgroups PHN and DPN were considered clinically relevant.

- PK Analyses is not included in this Statistical Analysis Plan, and will be done separately. PK Population is replaced with Per-Protocol population for subjects with NPRS assessments taken at timepoints in baseline and Week 4 visits.

13 Index of Tables, Listings and Graphs

Refer LAT-NP-001_Data Display Plan (Ver: 2.00) for the list of Tables, Listings and Graphs.

14 References

1. ICH. ICH Harmonized Tripartite Guideline: Statistical Principles for Clinical Trials E9. 1998.
2. ICH. ICH Harmonized Tripartite Guideline: Structure and Content of Clinical Study Reports E3. 1995.

15 Appendices

15.1 painDETECT questionnaire

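### SAP 11.6.2.5 and SAP Section 12 define the NPRS baseline-covariate analysis differently: one adds clinical diagnosis only, the other adds diagnosis and a second baseline covariate, most likely QST

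*SAP*

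**What the plan says.** - **SAP 11.6.2.5** says that the NPRS mixed model "will be repeated for the change from baseline in NPRS scores by including additional covariate: clinical diagnosis (PHN, DPN"). It leaves anything further to post hoc decisions after database lock. It names one covariate and one table (14.2.10.1).
- **SAP Section 12** lists how the current SAP departs from the protocol. It moves the NPRS regression "including clinical diagnosis (PHN, DPN) and baseline [REDACTED] as additional covariates is" from exploratory to secondary, on the ground that the PHN and DPN subgroups matter clinically. It names two covariates and gives no model statement.
- **SAP 7.5, endpoint 1** is the association of NPRS change with "selected subject baseline characteristics, including clinical diagnosis and pre-treatment" measures whose name is blacked out. Protocol 9.5 gives the same endpoint and names QST parameters.
- **Protocol 13.8** plans to relate NPRS change to "baseline parameters, such as the clinical diagnosis (PHN or DPN) and baseline QST parameters" and says that the SAP will give the approach.
- **Protocol 5.1**: "Quantitative sensory testing (QST) will be performed in up to 20 subjects (QST subjects"), and PK subjects take no part in it. SAP 4.1, with the test's name blacked out, still has a minimum of 20 where the protocol now has a maximum.

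**The concern.** Section 12 is not a log of superseded text. It states the current plan, so it and 11.6.2.5 should describe the same model. They do not, and each reading has a cost.

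Under Section 12 fitted as one model, a covariate that most subjects lack decides who is analysed. The diagnosis analysis, promoted because diagnosis was thought clinically relevant, would then rest on the tested subset. That subset is not a random sample of the trial: PK subjects are barred, and SAP Appendix 15.2 (test name blacked out) confines testing to sites with experience of the technique.

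Under 11.6.2.5, every subject stays in the diagnosis analysis, but the baseline-QST association has no specified model. It falls among the further analyses to be chosen after database lock, which is when protocol 7.13.2 allows the randomisation schedule to be disclosed.

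**Working it through.** **Inputs (protocol synopsis, Statistical Analysis; protocol 13.2).** SD of change 2, within-subject correlation 0.5, difference 1 NPRS unit, two-sided 5%, 44 evaluable, 20% dropout, 55 enrolled. QST subjects: up to 20 (protocol 5.1). PK subjects: 15, with no overlap.

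**1. The plan's own figure.** SD of the within-subject difference = sqrt(2 × 2² × (1 − 0.5)) = 2.0. The normal approximation gives n = ((1.960 + 1.282) × 2 / 1)² = 42.03, so 43. Noncentral-t power at n = 44 is 0.900. Enrolment = 44 / (1 − 0.2) = 55. The plan's figures reproduce.

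**2. Subjects kept if both covariates enter one model.** PROC MIXED omits any record with a missing covariate, and the SAP gives no imputation rule for this one.
- Protocol maximum: 20/44 = 45% kept, at least 24 of 44 (55%) lost. Against enrolment, 20/55 = 36% kept, 35 of 55 (64%) lost.
- If 20% of the 20 tested subjects drop out (assumption): 16/44 = 36% kept.
- Under the SAP 4.1 wording there is no upper limit except the PK exclusion: 55 − 15 = 40 could be tested, so at least 15 of 55 (27%) would be lost.

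A loss of more than half therefore rests on the protocol figure.

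**3. Effect on the diagnosis terms.** The diagnosis split is not given, so 50:50 is assumed, with 25:75 as a range.
- Main effect of diagnosis: SD of a subject's mean over two periods = sqrt(2² × (1 + 0.5) / 2) = 1.732. SE = 1.732 × sqrt(2/22) = 0.52 with 44 subjects and 1.732 × sqrt(2/10) = 0.77 with 20. Multiplying by 1.960 + 0.842 = 2.802, the difference detectable with 80% power goes from about 1.5 to about 2.2 units (25:75 split: 1.7 to 2.5).
- Treatment-by-diagnosis: SE = 2 × sqrt(2/22) = 0.60 with 44 and 2 × sqrt(2/10) = 0.89 with 20 (25:75 split: 0.70 and 1.03).

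**4. Effect on the treatment contrast in that model.** SE = 2/sqrt(n): 0.30 at n = 44, 0.45 at n = 20, 0.50 at n = 16. Power for 1 unit (n − 2 degrees of freedom): 0.90, 0.56 and 0.46. The 95% CI half-width is 0.61 at n = 44 and 0.94 at n = 20.

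**5. Deletion check.** In one simulated data set of 44 subjects with the second covariate missing in 24, the fit fell to 20 subjects. The SE of the diagnosis term rose from 0.50 to 0.86, and that of the treatment term from 0.29 to 0.39.

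**The case against.** The strongest reply is that 11.6.2.5 is the operative section. It adds a covariate that every subject has, so nobody is dropped. Section 12 is a summary bullet whose purpose is reclassification and whose reason concerns diagnosis alone. It does not say that the covariates share a model. This stands: the loss of subjects is conditional on one joint model without imputation. It does not remove the disagreement between two live sections.

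The second covariate's name is blacked out, so QST is an inference. It is a strong one, since the protocol analysis being reclassified pairs diagnosis with baseline QST parameters. The SAP also has blanks without marks (for example the heading of 11.6.3.1), so a hidden second covariate in 11.6.2.5 cannot be ruled out entirely. But that sentence is complete and names its covariate in the singular.

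Three stronger readings are tempting, and the documents do not support them.
- **That the trial's power falls from 90% to 56%.** That contrast is estimated by the primary model in SAP 11.6.1.2 in the PP population, repeated in FAS, and is untouched. The covariate analysis was never powered.
- **That the QST association will not be analysed.** 11.6.2.5 leaves room for further post hoc analyses. What is missing is prespecification.
- **That calling the analysis secondary contradicts SAP 3.3 and 7.5.** Section 12 declares and explains the change.

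Nor can it be said that the two sections give different results for Table 14.2.10.1. Only 11.6.2.5 cites that table, and the Data Display Plan is not among the documents.

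**Conclusion.** The point holds as a minor one. Two current sections of the SAP disagree on the covariates of a planned secondary analysis, and neither says whether a second covariate belongs in the same model or what happens to subjects without it. On one reading, at least 24 of 44 evaluable subjects leave the diagnosis analysis. On the other, the baseline-QST part of an exploratory endpoint has no prespecified model.

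The size rests on four assumptions: the blacked-out covariate is QST, the protocol's limit of 20 applies, both covariates enter one model, and nothing is imputed. The primary result does not depend on any of this.

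One further gap matters for the repair. SAP 3.3 asks how baseline characteristics relate to NPRS change on LAT8881 compared with placebo. A covariate entered only as a main effect does not answer that question under either section.

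**What to change.** Before unblinding, reword 11.6.2.5 and Section 12 so that both specify the same two separate models:

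1. Diagnosis model: all PP and FAS subjects, clinical diagnosis and treatment-by-diagnosis added, no sensory covariate.
2. Baseline-QST model: tested subjects only, the baseline QST covariate and its interaction with treatment added, n shown in the table, labelled exploratory.

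Change SAP 4.1 to agree with the protocol's limit of up to 20 tested subjects. The cost is a few lines of SAP wording and one extra exploratory table. No new data are needed.
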